## 4 Planned analysis

A flowchart according to the CONSORT statement will describe all patients randomized to the trial detailing withdrawals, drop-outs and inclusion in the analysis sets defined above. It will also provide details regarding treatment and assessment completion.

Standard methods of descriptive statistics will be used always indicating the number of valid values; frequencies, mean (standard deviation), minimum, maximum and/or quartiles (median [25%; 75%]), depending on the scale and distribution within the study population and/or per arm will be provided. Summary statistic will be reasonably rounded to avoid pseudo-precision. Reliability (Cronbach's  $\alpha$ ) will be calculated for each psychometric scale at T0.

For the explorative neurophysiological analyses, only completer analyses will be considered and in patients who have provided neurophysiological data on at least two sessions. There the primary focus is on understanding neurophysiological processes in those that complete the training sessions and its potential effect on outcome.

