#### 4.3.2 Within-session and between-session comparisons (CRED-nf 5b/5c)

The  $\beta$ -values for the two particular channels of each patients' individual ROIs will be analysed. Since the predicted time course in the first and second half of the regulation block and also between blocks is identical, a comparison of  $\beta$  amounts to a comparison of the optimal weighting of this predicted time course. As noted above, this can be difficult to interpret: e.g. an increase from 0.8 to 1 could indicate that the response followed the expectation both times with an increase in amplitude from 0.8 to 1, but it is also conceivable that there was good response to the stimulus the first time and none whatsoever with the higher value of  $\beta$ .

- $\beta$  will be displayed graphically for the first and second half of the average of all sessions
- The two  $\beta$  values per session will be averaged and displayed graphically per sessions
- $\beta$  will be analysed after standardization in a mixed linear model with the coefficients as the dependent variable. For the within-session analysis, the first and second half of the regulation condition will be estimated (fixed effect) and session (linear fixed effect) and patient as a random effect for the intercept. For comparisons between the tasks regulation and mirror, a mixed model with condition as the fixed effect of interest, session and first/second half as a nuisance parameter and patients as a random term will be used. These analyses will be repeated for the transfer vs mirror condition.

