### **4.4.2 Within-session and between-session comparisons (CRED-nf 5b/5c)**

Mean beta band activity in  $\mu\text{V}$  for baseline, feedback and transfer trial will be displayed graphically per session.

For within-session variability, two mixed effects models (one for feedback and one for transfer) will be used. The dependent variable is the mean power in the  $\beta$  band and the fixed effects are the (constant) baseline mean power in the  $\beta$  band and the number of the trial, treated as a numerical variable (i.e. assuming linear behaviour over time). The patient is the random term.

To assess the success of the feedback relative  $\beta$  band power will be shown graphically for resting state eyes open, eyes closed, and food cue presentation at pre and post treatment. Paired t-test of the logarithms of these values will be used for formal testing with Bonferroni-Holm correction for the three states.

For comparison with a “control” condition, the difference of  $\beta$  band power on a logarithmic scale (i.e. logarithm of the ratio) from feedback to its baseline will be compared to the difference from transfer to its baseline. These differences will be treated in a mixed model with condition (feedback vs transfer) and session number fixed effects along with their interaction and patient as a random variable. The interaction term will quantify a potential learning effect, i.e. that the feedback in the later sessions is no longer necessary and the difference between the conditions gets smaller.

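### The fNIRS half/session mixed model allows patients only a random intercept, and the other fNIRS and EEG mixed models leave the random structure open, so the error rate of their regulation and learning tests is not controlled in either direction

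*SAP*

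**What the plan says.** **fNIRS (SAP 4.3.2).** The within-session model has half as a fixed effect, with "session (linear fixed effect) and patient as a random effect for the intercept". This is the only model whose random part is stated to be the intercept. The regulation-versus-mirror model, repeated for transfer versus mirror, treats "session and first/second half as a nuisance parameter and patients as a random term will be used". Session is therefore a nuisance term there, and the random part is a bare patient term. The section does not settle whether the two channels are averaged before modelling.

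**EEG (SAP 4.4.2).** The two within-session models test "the number of the trial, treated as a numerical variable", contain no session term, and add "The patient is the random term". The feedback-versus-transfer model is set up "with condition (feedback vs transfer) and session number fixed effects along with their interaction and patient as a random variable", and its interaction is the learning test. The same section also plans paired t-tests of pre- and post-treatment relative beta power.

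**Elsewhere.** For the clinical T0–T1–T2 mixed model, SAP 4.2.2 states an unstructured covariance matrix. Nothing comparable is stated for the fNIRS or EEG models. On status, SAP section 4 says: "For the explorative neurophysiological analyses, only completer analyses will be considered". SAP 4.3 calls the fNIRS plan temporary and says it will be updated in the next SAP version.

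**The concern.** Each patient supplies many rows: up to 12 sessions by two halves, possibly by two channels and two conditions (fNIRS), or up to 12 feedback trials per session (EEG). A random intercept absorbs differences between patients in level, but not differences in the effect under test. If some patients regulate and others do not, the average effect is known only as well as the number of patients allows, while the model computes its standard error from the number of rows.

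The plan itself presupposes such differences. SAP 4.3.3 and 4.4.3 relate each patient's regulation success to binge-eating outcome, which makes sense only if patients differ in regulation.

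At stake is the statement that patients learned to regulate brain activity (CRED-nf items 5b/5c). The planned clinical comparisons are not at stake.

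**Working it through.** **Inputs from the documents.** 12 sessions (protocol 1.2.1). 26 patients randomised per arm with 20% dropout assumed, so about 21 remain (protocol synopsis, 7.4.3, 7.4.4). Two halves per condition and session (SAP 6.11.2). Two channels (SAP 4.3.2). Up to 12 feedback trials per EEG session (SAP 6.12.3). A 5% level (protocol 7.4.2; two-sided is assumed here). The plan states no variance component or error rate for these models, so there is no figure of its own to reproduce.

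**Assumed.** Row residual SD = 1; 24 patients; balanced data; no true mean effect. τ is the between-patient SD of the tested effect and ω the patient-by-session SD, both in residual SDs.

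**1. Two-level effects (half, condition).** With m rows per level per patient and n patients:
- true variance of the mean effect: (τ² + 2/m)/n
- variance used by the intercept-only model: about 2(1 + τ²/4)/(mn)
- SE ratio: r = √[(τ² + 2/m) / (2(1 + τ²/4)/m)], and n cancels
- rejection rate ≈ 2[1 − Φ(1.96/r)]

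Example, half test with channels averaged (m = 12), τ = 0.3: (0.09 + 0.1667)/0.1704 = 1.506, so r = 1.23, 1.96/1.23 = 1.59, and the rejection rate is about 11%.

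| Test (rows per patient) | r at τ = 0.2/0.3/0.5 | Formula | Simulation |
|---|---|---|---|
| Half, channels averaged (24) | 1.11/1.23/1.53 | 8/11/20% | 7/11/20% |
| Half, two channels as rows (48) | 1.21/1.43/1.94 | 10/17/31% | 10/17/32% |
| Condition, channels averaged (48) | 1.21/1.43/1.94 | 10/17/31% | 11/16/31% |
| Condition, two channels as rows (96) | 1.39/1.76/2.57 | 16/27/45% | 16/27/44% |

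At τ = 0 the rate is about 5%; at τ = 0.1 it is about 6–8%. Because n cancels, 21 or 26 patients give nearly the same results. The residual SD is that of one analysed row, so equal τ in the averaged and two-channel lines is not the same absolute variation.

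**2. Session trend.** Code session from −0.5 to 0.5, so that τ is the SD of the change over 12 sessions and Σx² = 143/121 = 1.18. With two rows per session, S = 2.36, 1/S = 0.423, and r² = (τ² + 1/S)/[(1 + τ²S/24)/S].
- τ = 0.5: 0.673/0.4335 = 1.55, r = 1.25, about 12% (simulation about 12%)
- τ = 1.0: 1.423/0.465 = 3.06, r = 1.75, about 26% (simulation about 28%)

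**3. Session-level variation alone (τ = 0).**
- Within-session contrast: r ≈ 1/√(1 + ω²). For ω = 0.5 and 1, r = 0.89 and 0.71, giving 2.8% and 0.6%. Simulated fNIRS rates run from about 3% down to 0.4%, so the test is conservative.
- Session trend with k rows per session: r = √[(1 + kω²)/(1 + ω²)]. For k = 2 this gives 1.10 and 1.22 (7.4% and 11.0%); for k = 4, 1.26 and 1.58 (12% and 21.5%). Simulated: 7.6% and 11.0%, then 13.4% and 22.8%.

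**4. Both sources, τ = 0.3.** At ω = 0.5 and 1, the half test with channels averaged rejects in 7.3% and 3.0%, and the condition test with two channels as rows in 21.6% and 13.2%.

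**5. EEG, if fitted with an intercept only.**
- Trial-number test (144 rows), SD of change across 12 trials 0.2/0.3/0.5: 12.0/19.2/35.5%.
- Condition-by-session interaction (24 rows), SD of change across 12 sessions 0.2/0.5/1.0: 5.1/7.0/11.4%.
- With ω alone at 0.5 and 1: trial test 2.6% and 0.3%; interaction 3.0% and 0.8%.

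**6. Patient-level alternative.** A t-test on one effect or slope per patient rejected in about 4–6% of simulations throughout.

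**The case against.** The case against runs as follows, and much of it stands.

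- **Wording.** A reader might infer that every fNIRS and EEG model is intercept-only. The SAP says so for one. A single patient term elsewhere does not exclude slopes, so intercept-only remains an inference there.
- **Direction.** A reader might infer that the standard errors are always too small. Working steps 1 and 3 show otherwise: no slope variation means no inflation, and omitted session-level variation pushes within-session tests the other way.
- **Likelihood.** A reader might infer that false learning findings are likely. The documents contain no variance components, so only a conditional range can be given. The EEG learning interaction is the least affected.
- **Other tests.** A reader might take these models as the only formal tests of regulation. For EEG that is wrong: the pre/post paired t-tests use one difference per patient and are immune.
- **Consequence.** The analyses are explorative and restricted to completers, and the fNIRS plan is provisional.

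Two possible defences do not help. The type I error remark in SAP 4.3 concerns poor fit of the first-level GLM. The AR-IRLS method in SAP 6.11.2 deals with serial correlation within a recording. Neither addresses differences between patients in the effect. Nor does conservatism from one omitted source rescue the test: the two errors cancel only by chance.

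**Conclusion.** The point holds in a limited form. One model has a random structure that does not support its tests if patients differ in the effect, and the remaining mixed models do not state theirs. Under intercept-only fits the true error rate could lie well below or well above 5%: from about 0.4% (within-session fNIRS tests, session-level variation only) to about 44% (condition test, two channels as rows, τ = 0.5). For the one explicitly intercept-only model with channels averaged, the half test reaches about 7/11/20% at τ = 0.2/0.3/0.5.

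These figures rest on assumed variance components, balanced data and 24 patients; only the patient number is immaterial. The consequence is confined to the mixed-model claims about regulation and learning. The primary endpoint is untouched. The change is still worth making, because the SAP already announces a revision of the fNIRS section and the correction is cheap.

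**What to change.** State the random structure separately for each model in SAP 4.3.2 and 4.4.2:

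- average the two fNIRS channels before modelling;
- add a by-patient random slope for the effect being tested (half, condition, trial number, session trend, or condition-by-session interaction);
- add a patient-by-session random intercept wherever several rows come from one session;
- use Satterthwaite or Kenward-Roger degrees of freedom;
- if the fit is singular, compute each patient's mean difference or slope and apply a one-sample t-test.

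The cost is a few lines of SAP text and changed model formulas, with no new data. Confidence intervals will usually be wider. In the fallback, patients with few sessions contribute imprecise slopes at equal weight, which the report should mention.

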### **4.3.3 Correlation between regulation and outcomes for patients who provided data for at least two feedback sessions (CRED-nf 6b)**

A linear model will be used with the number of OBEs at post-assessment as the dependent variable, the value at T0 as covariate and mean picture size across all sessions as the variable of interest.

## **4.4 Analysis of EEG data**

The pre-processing of the EEG data follows standard procedures and is described below (see appendix 6.12). The resulting data available to us at pre and post feedback are mean power in each of three frequency bands ( $\theta$ ,  $\alpha$  and  $\beta$ ) per patient, and task. Moreover, during the pre and post visits as well as each session, mean power for the subset of the  $\beta$  band is available for each patient, condition and task that was used for feedback.

### **4.4.1 Regulation success based on the feedback signal (CRED-nf 5a)**

The proportion of successful feedback and transfer trials, defined as trials with mean subset of the beta band values below the baseline value will be reported per session. Whereas in the case of NIRS, data were available on the amount of time in which the participant was successful per session, here only a single mean power value is available.

### **4.4.2 Within-session and between-session comparisons (CRED-nf 5b/5c)**

Mean beta band activity in  $\mu\text{V}$  for baseline, feedback and transfer trial will be displayed graphically per session.

For within-session variability, two mixed effects models (one for feedback and one for transfer) will be used. The dependent variable is the mean power in the  $\beta$  band and the fixed effects are the (constant) baseline mean power in the  $\beta$  band and the number of the trial, treated as a numerical variable (i.e. assuming linear behaviour over time). The patient is the random term.

To assess the success of the feedback relative  $\beta$  band power will be shown graphically for resting state eyes open, eyes closed, and food cue presentation at pre and post treatment. Paired t-test of the logarithms of these values will be used for formal testing with Bonferroni-Holm correction for the three states.

For comparison with a “control” condition, the difference of  $\beta$  band power on a logarithmic scale (i.e. logarithm of the ratio) from feedback to its baseline will be compared to the difference from transfer to its baseline. These differences will be treated in a mixed model with condition (feedback vs transfer) and session number fixed effects along with their interaction and patient as a random variable. The interaction term will quantify a potential learning effect, i.e. that the feedback in the later sessions is no longer necessary and the difference between the conditions gets smaller.

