	
Control intervention (1): 12 sessions (60 min) over 8 weeks of electroencephalography (EEG) neurofeedback (high beta training)
 
Control (2): 8 weeks without treatment, after which 12 sessions (60 min) over 8 weeks of fNIRS neurofeedback will be offered (delayed treatment control condition)

Primary outcome:	The number of objective binge-eating episodes (OBEs) over the past 14 days at post-treatment (t1), derived from the Eating Disorder Examination, will be compared between groups, correcting for the baseline value
Secondary outcome:	
 
- Feasibility including recruitment, attrition, assessment completion, patients' program evaluation
 
- Eating disorder psychopathology
 
- Executive functioning
 
- Weight management behavior
 
- Mental and physical health
 

Biometry:	
Efficacy / test accuracy: The comparison between the groups with respect to binge eating episodes directly after treatment.
 
Safety: Report of type and frequency of adverse events.
 
Secondary endpoints: Descriptive analyses, effect sizes, presented with 95% confidence intervals, parametric or non-parametric tests, regression analyses.

Trial duration:	
Duration of intervention per patient: 8 weeks
 
Follow-up per patient: 6 months
 
First patient in to last patient out (months): 25 months
 
Duration of the entire trial (months): 30 months
 
Recruitment period (months): 17 months

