In order to specifically target these neurobehavioral difficulties, brain-directed treatments for BED are being developed. Neurofeedback – a form of biofeedback – is one brain-directed approach with most of its empirical support in the treatment of ADHD, and initial evidence in substance use disorder. In EEG neurofeedback treatment, participants learn to regulate their brain activity (e.g., downregulate high beta activity), using online feedback through a brain-computer interface and operant conditioning. Initial evidence exists on the efficacy of EEG neurofeedback using food stimuli to reduce overeating tendencies in subclinical samples of restrained eaters. While EEG neurofeedback has several clear advantages, such as low cost, high portability, and high disseminability into clinical practice, the resolution is lower than with neurofeedback based on functional imaging methods, theoretically allowing for training of circumscribed brain areas. Proof-of-concept studies are emerging for real-time fMRI

neurofeedback using food cues in healthy individuals; however, evidence for clinical populations including BED is lacking, and related to high cost, its disseminability into clinical practice is questionable.

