### 6.12.3. EEG session-wise recording

During each session, beta band activity at baseline and during each trial were output from the neurofeedback device (in  $\mu\text{V}$ ) and manually noted for the neurofeedback and transfer condition. For each participant, the number of successful trials, defined as trials with a beta band activity below the baseline activity, with a possible range between 1-12 (for neurofeedback) and 1-6 (for transfer) trials, and condition-wise (i.e., for the neurofeedback and transfer condition) contrasts between regulation and baseline will be provided.

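### The EEG condition-by-session interaction cannot by itself show that feedback is no longer needed: fading regulation under feedback gives the same value as transfer catching up

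*SAP*

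**What the plan says.** The last paragraph of SAP 4.4.2 sets up a comparison with a control condition inside the EEG arm. The difference in log beta power "from feedback to its baseline will be compared to the difference from transfer to its baseline". The mixed model has "condition (feedback vs transfer) and session number fixed effects along with their interaction and patient as a random variable". One coefficient is then given a meaning: "The interaction term will quantify a potential learning effect, i.e. that the feedback in the later sessions is no longer necessary". The pattern that goes with this reading is that "the difference between the conditions gets smaller".

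The direction of success is clear from two other places. SAP 4.4.1 counts successful trials, "defined as trials with mean subset of the beta band values below the baseline value", and SAP 6.12.3 does the same, "defined as trials with a beta band activity below the baseline activity". A negative log ratio therefore means successful regulation, and a negative session slope means that regulation is getting better.

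The SAP does not interpret the session slope within either condition. It does not require that a narrowing gap come from better transfer, and it does not say which condition is the reference level.

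**The concern.** A gap between two lines can close because either line moves. The SAP's sentence assumes that the transfer line falls to meet the feedback line. If patients instead lose regulation under feedback, through habituation or fatigue, while transfer never improves, the coefficient looks the same and the SAP's sentence would describe it as feedback having become unnecessary. Loss of response over sessions is not far-fetched in this trial: SAP 4.3.1 notes that the picture set in the fNIRS arm was changed after session 6 because of habituation, although that is the other arm.

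At stake is the mechanistic account of the EEG arm. A deterioration could be written up as a training success.

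**Working it through.** **Inputs from the documents.** The outcome is the log ratio of beta power to its own baseline, and the terms are condition, session, their interaction and a random patient term (SAP 4.4.2). Success is beta below baseline (SAP 4.4.1, 6.12.3). There are 12 sessions and 26 patients per arm (Protocol synopsis).

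**Assumed, because the documents give no EEG effect size or SD.** The starting feedback-transfer gap is -0.20 log units. For the simulation only, the patient SD is 0.20 and the residual SD 0.25.

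The plan gives no power or effect figure for this interaction, so there is none to reproduce.

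**Step 1: what the coefficient is.** Code feedback as 1 and transfer as 0:

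y = b0 + b1·feedback + b2·session + b3·feedback·session + patient effect

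- Transfer slope = b2
- Feedback slope = b2 + b3
- Interaction b3 = feedback slope − transfer slope

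This identity holds whatever the effect sizes or variances.

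**Step 2: noise-free trajectories.** Sessions 1 to 12 span 11 steps, so a change of 0.20 is 0.20/11 = 0.0182 per session.

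| Case | Feedback, session 1 to 12 | Transfer, session 1 to 12 | Feedback slope | Transfer slope | Interaction b3 |
|---|---|---|---|---|---|
| A. Transfer catches up | -0.20 to -0.20 | 0 to -0.20 | 0 | -0.0182 | 0 − (−0.0182) = +0.0182 |
| B. Regulation under feedback lost | -0.20 to 0 | 0 to 0 | +0.0182 | 0 | 0.0182 − 0 = +0.0182 |
| C. Parallel improvement | -0.20 to -0.40 | 0 to -0.20 | -0.0182 | -0.0182 | 0 |
| D. No change | -0.20 to -0.20 | 0 to 0 | 0 | 0 | 0 |
| E. Both worsen, feedback faster | -0.20 to +0.10 | 0 to +0.10 | +0.0273 | +0.0091 | +0.0182 |
| F. Both improve, feedback faster | -0.20 to -0.50 | 0 to -0.10 | -0.0273 | -0.0091 | -0.0182 |

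A, B and E share one interaction, but only A fits the SAP's reading. C and D share another: zero says that the gap was constant, not whether anyone improved. The two slopes, read together, separate all six cases.

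**Step 3: does sampling variation change this?** The model was fitted to 200 simulated data sets per case (26 patients, random patient intercept, SDs as assumed above). The interaction was significant at 5% in 88% of data sets for A, 86% for B, 5% for C, 7% for D, 87% for E and 89% for F (in the opposite direction). A significant positive interaction is thus about as likely under lost regulation as under transfer catching up.

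**The case against.** The best defence has four parts.

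1. The SAP speaks of a potential effect and sets no threshold or decision rule. That is true and lowers the stakes, but the sentence still attaches one meaning to one coefficient.
2. The information needed to tell the cases apart is already planned. SAP 4.4.2 plots baseline, feedback and transfer activity session by session, SAP 4.4.1 reports success proportions per session for both trial types, and the model itself contains a session term. A careful reader would probably see case B in the graphs. However, these outputs are descriptive, the SAP does not link them to the interpretation, and the session coefficient is the slope of whichever condition happens to be the reference. They limit the harm without correcting the stated reading.
3. CRED-nf item 5c asks for a statistical comparison with a control condition, and the SAP's checklist points to 4.4.2 for it. Replacing the interaction by slopes against each condition's own baseline would weaken that comparison. This stands, so the interaction should stay.
4. A reader might infer that the model misses real learning whenever patients improve equally with and without feedback (case C). The SAP does not support that criticism. It limits the construct to growing independence from feedback, and for that question zero is the right answer when the gap does not change. What remains is a caution for reporting: such a zero should be called no convergence, not no learning.

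**Conclusion.** The point holds in a limited form. The interaction equals the feedback slope minus the transfer slope, so on its own it cannot support the conclusion that feedback is no longer needed. This rests on algebra and needs no assumption about effect size. The +0.0182 per session and the 88% and 86% rejection rates are illustrations under assumed values and do not show how likely a misreading is in this trial.

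Three stronger inferences should not be drawn:

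- That this is the SAP's only test of change over EEG training. Section 4.4.2 also plans pre-post paired t-tests of relative beta power in three states with Bonferroni-Holm correction, although these do not test regulation during the sessions.
- That it undermines the specificity question for which the EEG arm exists. The Protocol addresses that by comparing fNIRS with EEG neurofeedback, and section 4 of the SAP labels the neurophysiological analyses explorative.
- That the definition of success in SAP 4.4.1 is wrong. It contains no error.

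The primary endpoint is unaffected.

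**What to change.** Amend the last paragraph of SAP 4.4.2 as follows.

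- Keep the condition-by-session interaction as the control-condition comparison, and describe it as measuring convergence of the two conditions.
- State the reference coding. With transfer as reference, the transfer slope is b2 and the feedback slope is b2 + b3.
- Report both session slopes from this model with 95% confidence intervals.
- Interpret a narrowing gap as feedback no longer being necessary only when the transfer slope is negative, that is, when beta in transfer trials falls further below its baseline over sessions. Say whether this is judged on the estimate or on the interval.
- Show the feedback slope and its interval beside it, and describe narrowing that comes from lost regulation under feedback as exactly that.
- State that an interaction near zero means no convergence and is not evidence that no learning took place.

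This costs nothing beyond SAP wording. Both slopes are linear combinations of coefficients already in the planned model, so no new data, model or patients are needed.
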